8.1.5 CONTROLLED HUMAN MALARIA INFECTION

CHMI with cryopreserved, aseptically prepared vialled infectious Pf sporozoites from the 7G8 clone (PfSPZ Challenge (7G8)) will occur by direct venous inoculation.

Prior to CHMI, the following activities and procedures will be performed:

- Inclusion and exclusion criteria will be reviewed
- Medical history, AEs and SAEs will be updated to include concomitant medications, a directed physical examination will be performed (if indicated), and vital signs will be recorded
- Results of pregnancy test (urine or blood β -HCG) will be confirmed. CHMI will not proceed unless a negative pregnancy test has been obtained within 24 hours of CHMI.
- Blood samples will be collected for:
 - Safety: CBC with differential, creatinine and ALT
 - Immunological assays: refer to Section 8.2.3 'Immunology Laboratory Evaluations'

- Participants will be asked to verify and confirm their telephone contact information at this time, and the importance of maintaining contact and following study procedures will be re-emphasized.

Following CHMI, participants will remain at the clinical center for an observation period of at least 30 minutes. This will allow the study team to confirm that there are no immediate reactions in response to injection of PfSPZ Challenge (7G8) and to provide immediate care if any reactions do occur. After the 30-minute observation period, an assessment will be performed including the measurement of temperature, pulse rate, and blood pressure, local and systemic reactions from PfSPZ Challenge. Participants will be instructed to contact the clinical investigator if they experience any medical problems.

Participants will be instructed on the symptoms of malaria and complications of malaria to include, but not limited to, fever (oral temperature of $\geq 38^{\circ}\text{C}$ [$\geq 100.4^{\circ}\text{F}$]), subjective fever, chills, rigors (shaking chills), sweats, cough, headache, dizziness, malaise/fatigue, arthralgia, myalgia, nausea, vomiting, abdominal pain, diarrhea, chest pain, shortness of breath, palpitations. Participants will be assessed for signs and symptoms of malaria from +7 days post CHMI through +28-day post CHMI or until the participant becomes parasitemic, is treated and is asymptomatic.

Memory Aid

Participants will be provided with a daily memory aid on the day of PfSPZ Challenge. They will be asked to fill out the memory aid once a day starting on the day of CHMI and continuing for 6 days following PfSPZ Challenge. Participants will be asked to record temperature, local and systemic symptoms daily. The study staff will review the memory aid on the visit at 7 days post PfSPZ Challenge. The memory aids will be collected by the study staff but not considered as source documents. They will be used to help identify solicited AEs during the post-PfSPZ Challenge period. Failure by the participant to return a memory aid will not constitute a deviation. These results will be annotated in the participant's study file and/or CRFs.

8.1.6 POST-CHMI FOLLOW-UP VISITS

8.1.6.1 +7 THROUGH +18 DAYS POST-CHMI

To facilitate daily close monitoring of clinical status and malaria diagnostics, all participants who underwent CHMI will be seen daily at the CVD starting + 7 days after CHMI until + 18 days after CHMI or until the participant finishes his/her anti-malarial treatment. Participants will be required to remain vigilant about maintaining lines open for rapid communication with the study team. A study physician will be available for consultation 24 hours per day.

The following will occur at each visit:

- Vital signs will be recorded.
- Medical history, AEs, SAEs and concomitant medication update.
- Targeted physical exam (if indicated).
- Participants will be assessed for signs and symptoms of malaria as mentioned in Section 8.3.1.2 "Malaria Events". Signs and symptoms of malaria infection will be collected on the visit CRF specific to CHMI follow-up and will not be considered as adverse events.
- Unsolicited AEs will be recorded through 28 days post-CHMI.
- Collection of blood samples for qRT-PCR.

- Symptomatic study participants may have blood samples for qRT-PCR collected as frequently as every 6-8 hours or at any time post-CHMI based upon the clinical judgment of the investigator
- Blood collection for qRT-PCR will be discontinued upon malaria diagnosis and treatment.
- The clinical center will have the capability to prepare and read TBS. (See Section 8.2.3.5 'Thick Blood Smear (TBS)').

8.1.6.2 MANAGEMENT AND TREATMENT OF MALARIA PARASITEMIC PARTICIPANTS

Malaria infection will be treated when the criterion for a case is met. The case definition in this protocol identifies cases of malaria before gametocytes can develop. Detection of 2 positive qRT-PCR results at any level of parasitemia from samples collected \geq 12 hours apart will constitute a diagnosis of malaria. In the case of an acutely ill participant for whom the site PI (or designee) determines rapid diagnosis should be implemented, TBS may be utilized for diagnosis. If diagnosed, the study participant will be called to return to the clinical center to receive treatment. After completion of treatment participants will be asked to return to the clinical center +28 days post-CHMI.

- Safety laboratories will be drawn at time of diagnosis and at any other time point post-CHMI when deemed clinically indicated by the investigator.
- Just prior to the first dose of antimalarial medication, samples for preparation of TBS (to be read retrospectively) and confirmatory PCR will be collected.

All participants who develop blood-stage malaria infection will be treated with a standard dose of Malarone® (250 mg atovaquone/100 mg proguanil tablets) 4 tablets once per day for 3 days, as first line therapy. This will be done by directly observed treatment (DOT); that is, a study team physician or nurse will witness the swallowing of the Malarone® dose by the participant. In the event that a participant is allergic to, or unable to tolerate Malarone®, he or she will be treated with Coartem® (artemether/lumefantrine 20/120 tablets), an alternative, but equally effective, antimalarial agent; the adult dose for Coartem is 4 tablets orally twice daily for 3 days, with the first two doses on the day of parasitemia to be administered approximately 8 hours apart. The first dose each day will be administered by DOT whereas the second dose each day can be self-administered by the participant. Participants will be reminded of the potential side effects of the antimalarial treatment. All participants exposed to malaria will be unable to donate blood for 3 years.

If symptoms develop, provided there are no contraindications, participants may be given acetaminophen or ibuprofen. In case of vomiting, particularly if it interferes with the administration of antimalarial medication, participants can be treated with prochlorperazine or ondansetron. Antimalarial medication administration will be repeated once if vomiting occurs within 30 minutes of initial administration. If vomiting occurs twice, an alternative antimalarial treatment will be selected (see above).

8.1.6.3 +20, +22 AND +25 DAYS POST-CHMI

Participants who remain negative for patency +18 days post-CHMI will be followed and evaluated during visits that occur +20, +22, and +25 days after CHMI. The evaluation of participants will include:

- Vital signs, medical history, concomitant medication, AEs, SAEs update, collection of unsolicited AEs and directed physical exam (if indicated)
- qRT-PCR

- Solicited signs and symptoms of malaria
- Safety labs may be drawn if clinically indicated.

Any participants who develop blood-stage malaria infection as measured by qRT-PCR will be treated as outlined above.

8.1.6.4 +28 DAYS POST-CHMI

This follow-up visit shall include:

- Vital signs, medical history, concomitant medication, AEs, SAEs update, collection of unsolicited AEs and directed physical exam (if indicated)
- qRT-PCR
- Solicited signs and symptoms of malaria
- CBC with differential, ALT and creatinine
- Immunology Assays: Refer to Section 8.2.3 'Immunology Laboratory Evaluations'

Any participants who develop blood-stage malaria infection as measured by qRT-PCR at this visit will be treated as outlined above.

8.1.6.5 FINAL VISIT: +56 DAYS POST-CHMI

Participants will have medical history and concomitant medication update, vital signs taken and directed physical exam performed (if indicated). Any AEs or SAEs that are unresolved at that time will be continued to be followed until resolution or stabilization, or, if a serious or chronic condition has developed, until it has stabilized.

8.1.7 UNSCHEDULED VISITS

Unscheduled visits, requested by the participant or the study physician, may prompt a medical history update, vital signs, clinically indicated laboratory tests, documentation of any AEs, and/or any other medically indicated diagnostic or therapeutic procedures. A targeted physical examination (if indicated) may be conducted.

8.1.8 EARLY TERMINATION VISIT

If a participant wishes to end their participation early, and is willing to have evaluations performed, a physical examination may be performed, and blood may be collected for safety laboratory analysis, qRT-PCR, and/or immunology assays.

Investigators will make every effort to continue follow-up visits for any participant who has received one or more immunizations for the duration of the study even if it is determined that subsequent immunizations should not be administered.

8.1.9 MEDICAL CARE FOR RESEARCH RELATED INJURY

All study-related medical care will be provided without cost. Should a participant be injured as a direct result of participating in this research project, he or she will be provided medical care by the clinical center at no cost to the participant, for that injury. The participant will not receive any injury compensation, only

medical care. The participants will not be compensated for care if he/she chooses to seek care from his/her own physician.

If a participant is injured because of participation in this research the participant is entitled to free medical care for that injury at a hospital or clinic designated by the clinical center. If the participant receives care for research-related injuries outside of the designated hospital or clinic, the participant or the participant's insurance will be responsible for medical expenses.

For all participants: Transportation will not be provided from domicile to study location, hospitals, clinics, or the clinical center. No reimbursement is available if the participant incurs medical expenses to treat research-related injuries. No compensation is available for research-related injuries or lost time from work. The participant is not waiving any legal rights. The participant should contact the site PI if the participant believes he or she has sustained a research-related injury. The participant should contact the site PI for any questions.

Employees retain the right to pursue relief through established workers compensation processes, but these benefits are not guaranteed. This issue is addressed in the informed consent and will be discussed with the participant by the investigator or designee before the participant signs the informed consent to participate in the study. Requests for other benefits, such as compensation for lost time from work, are processed independently of this protocol.

8.2 EVALUATIONS: CLINICAL, IMMUNOASSAYS AND DIAGNOSTIC

8.2.1 CLINICAL EVALUATIONS

8.2.1.1 MEDICAL HISTORY

A medical history from childhood onward will be taken with special attention to neurologic disorders including seizures and migraine, recurrent infections that suggest immune suppression, previous history of splenectomy and prior vaccine reactions. Systems to be reviewed include head/eyes/ears/nose/throat, pulmonary, cardiovascular, gastrointestinal, genitourinary, skin, musculoskeletal, neurological, allergy/immunology, endocrine, and hematological.

8.2.1.2 ELECTROCARDIOGRAM

As part of the screening process, an ECG will be performed for potential participants and read by study physicians and/or consulting cardiologist. Participants with prolonged QT/QTc interval and those with other findings indicative of clinically significant cardiac disease will be excluded.

8.2.1.3 PHYSICAL EXAMINATION

As part of the screening process, study clinicians will perform a physical examination. Vital signs, including temperature, blood pressure and pulse, will be assessed with the physical examination. Subsequent physical examinations may be more targeted based on the need to evaluate for vaccine reactogenicity or any complaints noted by a participant, including suspected AE evaluation. Vital signs to be assessed at all follow-up visits are outlined by visit in the daily study procedures section.

8.2.1.4 ADVERSE EVENTS (AES) ASSESSMENTS

Solicited AEs:

PfSPZ Vaccine: Surveillance for solicited local AEs will be done for 2 days after each dose of PfSPZ Vaccine. Surveillance for solicited systemic AEs will be done for 7 days after each dose of PfSPZ Vaccine. The list of specific events is detailed in section 8.3.1.1.1 'Solicited Adverse Events'.

PfSPZ Challenge: Surveillance for solicited local AEs will be done for 2 days after the administration of PfSPZ Challenge using the same solicited AE list as is used for PfSPZ Vaccine. Surveillance for solicited systemic AEs will be done for 6 days after PfSPZ Challenge using the same solicited AE list as is used for PfSPZ Vaccine. Surveillance for malaria events will be done from 7 to 28 (CHMI+7 to CHMI +28) days after the administration of PfSPZ Challenge using an expanded list that include the expected signs and symptoms of malaria (See section 8.3.1.2 Malaria Events'). These events are expected as a consequence of Pf parasitemia and will not be considered adverse events.

Unsolicited AEs:

Unsolicited AEs will be collected within 28 days after immunization or CHMI. Collection of solicited and unsolicited AEs will be done before participants leave on the day of immunization and at scheduled visits post immunization. SAEs will be recorded throughout the study.

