9. Safety evaluation includes an electrocardiogram (ECG) performed at screening. Participants with abnormal cardiovascular symptoms or findings that appear clinically significant will be excluded and if appropriate, referred to a cardiologist for further evaluation; individuals with history of non-febrile seizures will also be excluded.
10. For the second and third immunizations, allowable windows are assigned (see Section 1.3 'Schedule of Activities').

³ FDA recommendation will be sought.

11. Solicited adverse events will be collected for 7 days after each immunization. The first six days after CHMI, solicited AEs will be assessed for a potential relationship to PfSPZ Challenge; beginning 7 days after CHMI solicited AEs will be assessed for a potential relationship to malaria infection if individuals develop parasitemia. Unsolicited adverse events will be collected from the first immunization (V1) until 21 or 28 days after the third immunization (V3), depending on the timing of CHMI, and for 28 days after CHMI. Physical exams and medical history will be assessed repeatedly as indicated. Safety laboratories will be collected at screening, day of V1, 7 days after V2, 14 days after V3, day of CHMI and 28 days after CHMI.
12. Surveillance for SAEs will occur for the duration of the study.
13. Follow-up of adverse events (including SAEs) and other clinical events will occur until resolution or stability.
14. Participants will be observed for 30 minutes following each dose of PfSPZ Vaccine or PfSPZ Challenge.
15. Clinical laboratory testing will be conducted by certified laboratories.
16. A Local Safety Monitor (LSM) will be assigned to the site, and a Safety Monitoring Committee (SMC) will provide safety oversight.
17. External monitoring will be performed.
18. Electronic case report forms (eCRFs) will serve as the repository of source documents and other relevant data for each study participant. Only information that cannot be collected initially into the CRF (for instance, EKGs and AE medical records) will first be collected onto separate source documents before transcription into the CRF. Laboratory results will be entered from source documents directly into the database.
19. Detection of parasitemia post CHMI will be based upon qPCR. Participants who have 2 positive qPCR results separated by greater than or equal to 12 hours or a single qPCR result reading > 250 estimated parasites/mL will be treated with anti-malaria therapy.

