A syndromic classification will be used for unsolicited adverse events; e.g., cough, nasal congestion, sore throat will be combined and recorded as “upper respiratory tract infection.” Thus, whenever applicable, the term for the unifying diagnosis will be recorded as the adverse event, not each individual sign or symptom.

Any event not included under the specific list for solicited local or systemic adverse events (see Section 8.3.1.1.1 ‘Solicited Adverse Events’) or malaria events (see Section 8.3.1.2 ‘Malaria Events’ below) will be captured as an unsolicited AE if the AE occurs within 28 days after immunization or CHMI. Events outside of this period will be collected as clinical events.

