8.3.1.2 MALARIA EVENTS

Starting at 7 days post-CHMI through either 28 days post-CHMI (CH+7 to CH+28) or 3 days after treatment commences for parasitemia, participants will be monitored for signs and symptoms consistent with malaria infection. These “Malaria Events” will be documented but will not be categorized as adverse events since they are expected outcomes of malaria infection.

Malaria Events (collected day CH+7 and onward during CHMI): Fever (oral temperature $\geq 100.4^{\circ}\text{F}$), subjective fever, chills, headache, fatigue, malaise, myalgia, arthralgia, rigors, sweats, cough, nausea, vomiting, dizziness, abdominal pain, diarrhea, chest pain, palpitations, shortness of breath, and tachycardia.

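### From CHMI+7 to +28, 20 listed symptoms are classed as malaria events and not AEs even in participants who stay qPCR negative, contrary to sections 4.1 and 8.3.1

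*Combined protocol and SAP*

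**What the plan says.** - **Classification.** Section 8.2.1.4 sets malaria-event surveillance from CHMI+7 to CHMI+28 and states: "These events are expected as a consequence of Pf parasitemia and will not be considered adverse events". Section 8.3.1.2 says the events "will be documented but will not be categorized as adverse events since they are expected outcomes of malaria infection". Section 8.1.6.1 has them "collected on the visit CRF specific to CHMI follow-up and will not be considered as adverse events". None of these sentences depends on the qPCR result.
- **The list.** Section 8.3.1.2 names 20 items, starting with fever and headache and ending with "abdominal pain, diarrhea, chest pain, palpitations, shortness of breath, and tachycardia".
- **No other route for a single symptom.** Under Unsolicited Adverse Events (8.3.1.1.1.1), an event on neither the solicited list nor the malaria list "will be captured as an unsolicited AE if the AE occurs within 28 days after immunization or CHMI". A listed symptom therefore does not qualify.
- **Text that reads differently.** Section 4.1 item 11: "beginning 7 days after CHMI solicited AEs will be assessed for a potential relationship to malaria infection if individuals develop parasitemia". Section 8.3.1 defines an AE as any adverse change from baseline after first product, related or not. Section 7.2 leaves Grade 3 AEs judged related to malaria out of the pausing count, which presupposes that such symptoms can be AEs with a relatedness judgement.
- **End of the window.** Section 8.2.1.4 uses day +28 for everyone. Section 8.3.1.2 has: "Starting at 7 days post-CHMI through either 28 days post-CHMI (CH+7 to CH+28) or 3 days after treatment commences for parasitemia". Section 8.1.5 uses day +28, or the point at which the participant has become parasitemic, been treated and is symptom-free.
- **What is still captured.** Section 8.2.1.4: "SAEs will be recorded throughout the study". Section 8.3.1.1.1.1 also records a unifying diagnosis, rather than its component symptoms, as the unsolicited AE.

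**The concern.** The justification given is that the symptoms follow from parasitemia. That cannot hold in someone who never becomes parasitemic, yet the rule is written for everyone who undergoes CHMI. A non-serious listed symptom with no diagnosis then has no AE category.

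The label has consequences. Section 8.3.5 requires severity, relationship, alternate etiology and outcome for each AE. Section 8.1.6.1 states no such fields for the CHMI visit form. Section 2.2.1.3 says a causal link between CHMI and cardiac events cannot be excluded, and asks about chest pain, palpitations and shortness of breath from day 7. From that same day these three symptoms stop being AEs, including in an uninfected participant.

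Staying uninfected is the efficacy outcome, so the mislabelled symptoms will not be spread evenly across the arms. Site staff and programmers also cannot apply 4.1, 8.2.1.4 and 8.3.1.2 together and reach one answer.

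**Working it through.** **Inputs.** Planning rates (9.2): 12/13 controls and 20/39 vaccinees infected, 83% power, VE 44.4%. Control infection in earlier 7G8 challenges (2.1.3): 27/28. Parasitemia appears on days 7 to 17 (2.2.1.3). V3 is day 29 and CHMI is day 50 or 113 (1.3, 8.2.3.1). Malaria-event windows as in 8.2.1.4 and 8.3.1.2.

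**1. The plan's own figures.** VE = 1 − (20/39)/(12/13) = 1 − 0.513/0.923 = 44.4%. Two-sided 5% z test with pooled null variance: difference 0.410, null SE 0.156, alternative SE 0.109; (0.410 − 1.96 × 0.156)/0.109 ≈ 0.96, power 83.2%. Both agree with 9.2.

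**2. Participants to whom the stated reason cannot apply.** Vaccinees: 39 − 20 = 19, or 48.7%. Controls: 13 − 12 = 1, or 7.7%. Vaccine share: 19/20 = 95%. With VE from 44.4% to 80% and control infection of 92.3% or 96.4%, the share runs from 95% to 99%. For example, at VE 80% and 27/28, negatives are 39 × (1 − 0.2 × 0.964) = 31.5 vaccinees and 13 × 1/28 = 0.46 controls; 31.5/31.9 = 98.5%.

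**3. Listed symptoms removed in total, by arm.**
- *Window of 8.2.1.4.* It is 22 days (+7 to +28) for everyone. Background symptoms are lost equally per participant. The vaccine share, 39/52 = 75%, is only the 3:1 allocation.
- *Window of 8.3.1.2.* Assume treatment starts on the day of diagnosis, so an infected participant's window lasts L = 4 days (diagnosis on day 7) to 14 days (day 17). Excluded days are 19 × 22 + 20L in vaccinees and 1 × 22 + 12L in controls.

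| L | Vaccine days (per person) | Control days (per person) | Per-person ratio |
|---|---|---|---|
| 4 | 498 (12.8) | 70 (5.4) | 2.4 |
| 14 | 698 (17.9) | 190 (14.6) | 1.2 |

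- *Symptoms caused by malaria.* These are removed from 51% of vaccinees and 92% of controls, so more per person in controls. Let m be the mean number of malaria-caused symptoms per infected participant and b the daily background rate. Under 8.3.1.2 the total losses per person are equal when m/b = (vaccine days − control days per person)/(0.923 − 0.513). This is 7.38/0.410 = 18 at L = 4 and 3.28/0.410 = 8 at L = 14. Above that, controls lose more. The documents give neither m nor b.

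**4. Overlap with the primary safety endpoint.** That endpoint concerns related events after vaccination (1.1). Unsolicited collection ends at V3+21 or V3+28 (4.1 item 11). By nominal schedule the malaria-event window is 50 + 7 − 29 = V3+28 to 50 + 28 − 29 = V3+49 in the 3-week cohort, and V3+91 to V3+112 in the 12-week cohort. The overlap is at most about one day, in the 3-week cohort, if the 28-day wording of 8.2.1.4 is used.

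**The case against.** The strongest reply is that the rule covers both arms and little of importance is lost. Serious events are recorded throughout. A respiratory infection, gastroenteritis or cardiac diagnosis is not on the list and would be an unsolicited AE. Section 3.1 calls for a work-up when a malaria-like illness is PCR negative, and section 2.2.3 has cardiac-type symptoms evaluated by an investigator. Section 9.4.4 describes AE comparisons over surveillance periods after immunization, and no post-challenge comparison between arms is defined. All of this stands. It limits the loss to isolated, non-serious, undiagnosed symptoms, but it does not give those symptoms a correct label in an uninfected participant.

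A reader might infer more than the documents support:
- *That AE counting is suppressed mainly in the vaccine arm.* The 95% share counts qPCR-negative people, not events. The total removed could be larger per person in either arm (step 3). Section 8.2.3.4 says treatment almost always precedes symptoms, which would make malaria-caused losses small, but no rate is given.
- *That listed symptoms turn back into AEs three days after treatment starts.* No section says so. The unsolicited-AE rule excludes by list membership and states no end date for the malaria list. The ratios of 1.2 to 2.4 apply only if that reversion is assumed.
- *That the primary safety result is biased.* Step 4 shows it is almost untouched.

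A further fair objection concerns the remedy. Counting listed symptoms as AEs only in negatives would condition on the efficacy outcome. With an assumed 20% background chance in both arms, it would give 0.20 × 19/39 = 9.7% of vaccinees against 0.20 × 1/13 = 1.5% of controls, a spurious 6.3-fold excess. That figure assumes infected participants contribute nothing over the whole 22 days, so a limited attribution window would shrink it. The objection still rules out that comparison between arms.

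**Conclusion.** The point holds as a classification defect and an internal contradiction. As written, three sections relabel 20 symptoms in participants to whom the stated reason cannot apply, and sections 4.1 item 11 and 8.3.1 read otherwise. At planning rates this concerns 19/39 vaccinees and 1/13 controls, so the wrongly labelled symptoms fall mainly among vaccinees. That rests on the infection rates in 9.2 and on broadly similar background symptom rates in the two arms. A net arm difference in events removed is not established. The consequence is for the post-CHMI safety data: non-serious symptoms without grade or relatedness, and a window that different readers would close on different days. It should be corrected, but it does not threaten the primary safety comparison.

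**What to change.** 1. Reconcile 4.1 item 11, 7.2, 8.1.5, 8.1.6.1, 8.2.1.4, 8.3.1, 8.3.1.1.1.1 and 8.3.1.2, with one end to the malaria-event window and a statement of how a listed symptom is classified after it.
2. Record every listed symptom from CHMI+7 to +28 in all participants, with grade and relatedness. Negative status is final only at day +28, so this must be collected prospectively in everyone.
3. Attribute a listed symptom to malaria only in participants who meet the parasitemia case definition (8.2.3.4), within a stated window around first positive qPCR and treatment. Treat it as an AE otherwise. State how participants meeting only the single-reading criterion in 4.1 item 19 are handled.
4. In the SAP, tabulate all listed symptoms by randomized arm over the common +7 to +28 window, flagged by qPCR status and timing. The arm comparison then does not condition on infection.

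The cost is wording, grade and relatedness fields on a form that already collects the symptoms, some extra AE form work, and one table.
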